7.1.4 Embryo Transfer Visit (Day 5 or Day 7 Post Randomization)

Subjects will return to the site 3 to 5 days after oocyte retrieval for embryo transfer. If the embryologist determines the embryos should be transferred at the cleavage stage, embryo transfer will occur on Day 5 Post Randomization. If the embryologist determines the embryos should be transferred at the blastocyst stage, embryo transfer will occur on Day 7 Post Randomization.

| | |
|------------------------|---|
| Substance Code | Clinical Performance and Safety Investigation of ENDO metrial Washing ME dicinal DE vice Forielle |
| Protocol Number | MS 700623_0009 |

The following procedures will occur at the Embryo Transfer Visit:

- Embryo transfer (maximum of 2 embryos will be transferred); if no embryos are available for transfer, the subject will exit the study and study exit procedures, as applicable, will be performed
- Provide luteal support/endometrial preparation (600 mg vaginal progesterone to be used daily from the day after Oocyte Pick Up day)
- Calculate the fertilization rate (number of zygotes divided by the number of mature (MII) oocytes inseminated)
- Record adverse events, device incidents and concomitant medications
- Schedule the Post Embryo Transfer Visit 1 (Day 14 Post Embryo Transfer)

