As appropriate, variables will be summarized descriptively (frequency and percentage will be summarized for categorical variables; mean, standard deviation [SD], median, and maximum will be presented for continuous variables) by study visit and by treatment group. All study data will be listed by subject. A detailed Statistical Analysis Plan (SAP) including dictionaries used for coding and software used will be prepared separately for interim and final analysis. Study final analysis will be performed by PPD and Interim analysis will be performed by a PPD independent statistician from a different geographical region. A firewall will be implemented to ensure interim results will not be accessible to any PPD staff except to the independent statistician who will perform interim analysis.

Forielle Clinical Performance

The primary endpoint, subject implantation rate, is defined as number of intrauterine gestational sacs divided by the number of embryos transferred, as assessed at PET Days 21 to 28. Mean subject implantation rate, as assessed at PET Days 21 to 28 in subjects treated with Forielle endometrial washing procedure, will be compared to the mean subject implantation rate in subjects who receive no endometrial washing (control group) following COS.

For the primary endpoint analysis addition to summary statistics, differences in mean subject implantation rate between study procedure and control procedure will be investigated and compared using Gamma/log normal regression model. The analysis model will include treatment procedure as the fixed effect and Embryo Transfer Day (Day 5 PR or Day 7 PR), age, number of follicles at baseline and number of embryos transferred per subject as covariates.

To evaluate the treatment comparison, estimated mean differences will be presented together with two-sided 95% confidence intervals and p-values. Appropriate distribution will be decided based on good ness of fit (residual sum of squares) value. This primary clinical performance endpoint analysis will be tested by planned group sequential design with O'Brien-Fleming type spending function. The study for clinical performance will be stopped at significance level of 0.003 in first (50% of subjects) interim analysis and at significance level 0.049 in final analysis.

Safety

Device incidents will be summarized using frequency and percentages for two treatment groups.

Table 1-1 Schedule of Assessments

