8.5 Description of Statistical Analyses

8.5.1 General Considerations

The study data will be reported using summary tables, figures, and data listings. Continuous variables will be summarized using mean, standard deviation (SD), coefficient of variation (CV%, as appropriate), median, minimum, maximum, and, as appropriate, geometric mean.

Descriptive statistics will be presented for key outcome measures. Categorical data will be summarized with the number of non-missing values and the numbers of values equal to each of the possible values. Percentages of subjects with each of the possible values will be calculated from the number of subjects in the corresponding analysis population, unless stated otherwise.

Unless otherwise specified, all formal statistical tests will be two-sided at the 5% significance level. Point estimates of treatment differences will be accompanied with two-sided 95% confidence intervals (CIs) where applicable. P-value will be used to draw statistical significant conclusions only for primary endpoint and for secondary endpoints all statistical estimates will be used for descriptive comparison.

In the case of normality assumption violations, appropriate non-parametric methods will be used for analysis.

All data will be presented in by-subject listings.

The statistical analysis will be performed using SAS[®] Version 9.2 or higher.

Substance Code Clinical Performance and Safety Investigation of ENDOmetrial Washing
MEdical DEvice Forielle
Protocol Number MS 700623_0009

All details regarding the statistical analysis and the preparation of tables, listings and figures will be described in a separate Statistical Analysis Plan (SAP) document developed by separately for interim and final analysis.

Study final analysis will be performed by PPD and Interim analysis will be performed by a PPD independent statistician from a different geographical region. A firewall will be implemented to ensure interim results will not be accessible to any PPD staff except to the independent statistician who will perform interim analysis.

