8.5.2 Analysis of Primary Endpoints

The primary endpoint subject implantation rate is defined as number of intrauterine gestational sacs divided by the number of embryos transferred, as assessed at PET Days 21 to 28.

Mean subject implantation rate as assessed at PET Days 21-28 in subjects treated with Forielle endometrial washing procedure will be compared to the mean subject implantation rate in subjects who receive no endometrial washing (control group) following COS.

For the primary endpoint analysis addition to summary statistics, differences in mean subject implantation rate between study procedure and control procedure will be investigated and compared using Gamma/log normal regression model. The analysis model will include treatment procedure as the fixed effect and Embryo Transfer Day (Day 5 PR or Day 7 PR), age, number of follicles at baseline and number of embryos transferred per subject as covariates.

To evaluate the treatment comparison, estimated mean differences will be presented together with two-sided 95% confidence intervals and p-values. Appropriate distribution will be decided based on good ness of fit (residual sum of squares) value.

This primary endpoint analysis will be tested by planned group sequential design with O'Brien-Fleming type spending function. The study for clinical performance will be stopped at significance level of 0.003 in first (50% of subjects) interim analysis and at significance level 0.049 in final analysis.

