8.6 Interim and Additional Planned Analyses

One interim analysis is planned and a Data Monitoring Committee (DMC) will review and give advice to the sponsor regarding the study conduct. The DMC will be comprised of a statistician and physician not part of the study and will be appointed prior to the planned interim analysis. The purpose of the DMC is to verify the reliability of the primary endpoint since the study is unblinded to the study investigator. Detailed procedures will be described in a DMC charter.

Interim analysis on PET Days 21 to 28 data will be conducted when 1,078 subjects have been through treatment procedure and followed for 21 to 28 days after embryo transfer for the primary analysis. An O'Brien-Fleming type boundary will be used to determine the nominal significance level with overall 5% two-sided significance level i.e., the nominal significance level for the interim analysis will be 0.003. Based on the interim finding, the DMC may recommend to stop the subject enrolment early for clinical performance considerations or to continue the study as planned. No further results of the interim analysis will be made available by the DMC until final analysis is done.

The final analysis will be done when 2,156 subjects have been through treatment procedure and followed for 70 to 84 days post embryo transfer and complete all the protocol planned procedures and the O'Brien-Fleming boundary will be used to determine the nominal significance level with overall 5% two-sided significance level i.e. the nominal significance level for the final analysis will be 0.049.

9 Ethical and Regulatory Aspects

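### The primary and both secondary models, as specified, have no place for a randomised woman with no embryo to transfer, and no analysis set is named for them

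*Combined protocol and SAP*

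**What the plan says.** Randomisation takes place on the HCG triggering day (sections 7.1.2.3 and 8.2), about two days before retrieval and five or seven days before transfer. Section 7.1.4 provides for failure to reach transfer: "if no embryos are available for transfer, the subject will exit the study and study exit procedures, as applicable, will be performed".

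Section 8.3.1 defines the primary endpoint as intrauterine sacs over embryos transferred. Under section 8.5.2, "differences in mean subject implantation rate between study procedure and control procedure will be investigated and compared using Gamma/log normal regression model". On covariates it continues: "The analysis model will include treatment procedure as the fixed effect and Embryo Transfer Day (Day 5 PR or Day 7 PR), age", followed by follicle number and number of embryos transferred. Section 8.5.3 puts transfer day, age and follicle number in the logistic models for Day 14 pregnancy and ongoing pregnancy.

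Section 8.4 defines ITT as everyone randomised, analysed by assigned arm. Neither 8.5.2 nor 8.5.3 says which set it uses, and 8.5.2 describes the groups by the procedure received.

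Section 8.6 places the interim "when 1,078 subjects have been through treatment procedure and followed for 21 to 28 days after embryo transfer for the primary analysis". For the end of the study: "The final analysis will be done when 2,156 subjects have been through treatment procedure and followed for 70 to 84 days post embryo transfer".

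Details are deferred. The synopsis says: "A detailed Statistical Analysis Plan (SAP) including dictionaries used for coding and software used will be prepared separately for interim and final analysis". Section 8.5.1 says: "All details regarding the statistical analysis and the preparation of tables, listings and figures will be described in a separate Statistical Analysis Plan". Neither SAP is in the supplied text.

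**The concern.** A woman can be randomised and then have nothing to transfer. ITT includes her, but the primary endpoint gives her no value and the models need covariates that she does not have. Fitted in the ordinary way, the models would compare women selected by an event after open-label allocation, and the protocol would not have said so.

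Most of the weight falls on the primary analysis, since "for secondary endpoints all statistical estimates will be used for descriptive comparison". An analysis of transferred women has a legitimate place: section 5.2 chose the implantation rate to study receptivity. But it should be a named estimand and not a by-product of undefined inputs. If the no-transfer share differed between arms, the two analyses would answer different questions with different numbers, and the choice should be fixed before interim data are seen.

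**Working it through.** **1. What each model needs and what she has**

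- Primary outcome: 0 sacs / 0 embryos, undefined.
- Embryo Transfer Day: two levels only, so missing in all three models.
- Number of embryos transferred (primary model): 0, but without a defined outcome or transfer day.
- Day 14 result: the test is timed from a transfer that did not happen.
- Ongoing pregnancy: the Note in section 5.5 on entering negative ultrasounds may be read as giving her a no. Here she would be lost through the transfer-day covariate alone.

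Complete-case fitting therefore drops her three times.

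**2. Scoring her 0 is not enough.** Gamma and log-normal distributions have positive support. Zero is also the rate of every transferred woman without a sac: at the protocol's rates, with single transfers, 1 − 0.25 = 75% of controls and 1 − 0.31 = 69% of the Forielle arm.

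**3. Triggers.** 2 × 916 = 1,832 and 1,832 / 0.85 = 2,155.3, rounded up to 2,156, reproducing section 8.1. The final trigger thus equals the whole randomised number. With no replacement and no other loss, 2,156 × (1 − s) women can be followed from a transfer: at most 2,091, 2,048, 1,940 or 1,832 for s = 3%, 5%, 10% or 15%. Section 5.5 mentions replacements only if dropout exceeds 15%. The interim trigger of 1,078 stays reachable.

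**4. Power if she is kept at 0.** The documents give no no-transfer share. Shares below are assumptions, equal in both arms, inside the 15% allowance; other losses are excluded.

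Method: two looks at information 0.5 and 1, bounds 2.96259 and 1.96857 (section 8.1), pooled variance and continuity correction. With k women per arm at a look and p̄ = (p1 + p2)/2, the expected statistic is (p2 − p1 − 1/k) / √(2p̄(1 − p̄)/k). The two statistics have correlation √0.5.

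Check: 916 per arm, 0.25 against 0.31, gives expected statistics 1.949 and 2.808 and power 0.8002; the protocol states 0.80025.

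With no-transfer share t and other loss o: n = 1,078(1 − o), f = 1 − t/(1 − o), rates 0.25f and 0.31f.

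| t + o | n per arm | rates | power |
|---|---|---|---|
| 0 + 15% | 916.3 | 0.2500, 0.3100 | 80.0% |
| 3 + 12% | 948.6 | 0.2415, 0.2994 | 79.5% |
| 5 + 10% | 970.2 | 0.2361, 0.2928 | 79.2% |
| 10 + 5% | 1,024.1 | 0.2237, 0.2774 | 78.4% |
| 15 + 0% | 1,078 | 0.2125, 0.2635 | 77.8% |

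A linear model of the subject rate (same bounds, unpooled variance, no continuity correction, no covariate gain, all transfers single) gives 81.6%, 81.1%, 80.8%, 80.1% and 79.4% for the same rows.

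**5. Unequal shares, illustration only.** Assume no-transfer shares of 5% in control and 10% with Forielle. Among transferred women the difference is 0.06. Over all randomised women it is 0.31 × 0.90 − 0.25 × 0.95 = 0.279 − 0.2375 = 0.0415.

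**The case against.** The strongest reply is that the implantation rate is naturally a per-transfer measure. A woman with no embryo says nothing about receptivity, embryo evaluation is blinded (section 6.10), and the separate SAPs may settle the set. Part of this stands. A transferred-women estimand, named as primary with ITT beside it, would also close the gap. The SAPs may well name the set, but one that kept the protocol's endpoint, covariates and model could not include these women.

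Four stronger readings are tempting and the documents do not support them:

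- *The protocol excludes her.* It does not say so. The loss is inferred from undefined inputs under complete-case fitting. Section 7.1.3 has the transfer visit settled from the retrieval visit, so a planned day may exist for some women, although the models do not refer to a planned day.
- *No text touches her outcome.* The Note in section 5.5 may give her a negative ongoing-pregnancy result. It supplies no denominator, Day 14 result or transfer day.
- *The result would favour Forielle.* Allocation is open and the doctor shares the decision on number and stage of embryos (section 7.1.3), but the exit condition is that none is available and the laboratory is blinded. No direction can be claimed.
- *Both triggers fail because of these women.* Only the final one is unreachable, and any unreplaced loss makes it so.

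The zero-rate problem also exists apart from non-transfer. It belongs here because a zero score cannot work until the model changes. The non-parametric fallback in section 8.5.1 names no method and is tied to normality violations.

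**Conclusion.** The point holds as a gap between the ITT definition and the three models, and it should be corrected. On the supplied text, a randomised woman with no embryo available has no primary outcome and no transfer day, no set is named, and ordinary fitting would leave an analysis of transferred women. Two defects stand on the text alone: the specified distributions cannot take rates of 0, and the final trigger equals the number randomised, with 15% loss already allowed for.

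The bias, if any, cannot be sized or signed. The cost of including these women is small: at most 2.2 percentage points of power (80.0% to 77.8%), assuming equal shares of up to 15% within the planned loss and other losses excluded. A reader might infer that the trial is too small; these figures do not show that.

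**What to change.** 1. Name ITT, by randomised arm, as the primary set for sections 8.5.2 and 8.5.3, and describe the groups in 8.5.2 and the synopsis by assignment, not by procedure received.
2. In ITT, score a woman with no embryo available for transfer as implantation rate 0 and not pregnant at Day 14 and at Days 70-84. State one rule for women who have embryos but whose transfer is cancelled or who withdraw before it, and one for unknown outcomes. Tabulate by arm in the same categories.
3. Remove Embryo Transfer Day and number of embryos transferred from the ITT models; keep age and follicle number.
4. Replace the Gamma/log-normal model by one that takes zeros, for example linear regression of the subject rate with robust standard errors. This gives the mean difference and interval that section 8.5.2 asks for.
5. Keep a named transferred-women analysis as supportive for the receptivity question in section 5.2. If the sponsor prefers it as the primary estimand, say so and report ITT beside it.
6. Reword the section 8.6 triggers to count randomised women whose outcome is known or who have left the study.

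The cost is a protocol amendment carried into both SAPs. Withdrawal reasons are already recorded under section 5.5, so the added data work is mainly to categorise the reason for no transfer. Restate the power as about 78% to 79.5% under the assumed shares. Holding 80% on the protocol's test would take 2,184 to 2,276 women, 28 to 120 more than planned; there is no need to enrol them.

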7.1.5 Post Embryo Transfer Day 14 Visit (PET Day 14)

The following study assessments will be performed 14 days after embryo transfer at the Post Embryo Transfer (PET) Day 14 visit:

- Serum β -HCG pregnancy test
- Record adverse events, device incidents and concomitant medications

Serum β -HCG pregnancy test may be performed by another physician; however, the pregnancy test report must be provided to the investigator. In these cases, all other PET Day 14 assessments may be performed via telephone.

If the serum β -HCG pregnancy test is negative at PET Day 14, luteal support will be discontinued and the investigator will enter negative ultrasound results for ultrasound assessments that would have been performed at the PET Days 21-28 and PET Days 70-84/Weeks 10-12 visits.

If the serum β -HCG pregnancy test is positive at PET Day 14, luteal support will continue, remaining PET Day 14 assessments will be performed and the subject will be instructed to return to the centre for the PET Days 21-28 visit.

7.1.6 Post Embryo Transfer Days 21 to 28 Visit (PET Days 21-28)

Subjects with a negative serum β -HCG pregnancy test at PET Day 14 will be contacted via telephone 21 to 28 days after embryo transfer for the PET Days 21-28 visit. During this telephone visit, adverse events, device incidents and concomitant medications will be recorded. The investigator will ensure negative ultrasound results are recorded for ultrasound assessments that would have been performed at PET Days 21-28 and PET Days 70-84/Weeks 10-12.

Subjects with a positive serum β -HCG pregnancy test at PET Day 14 will return 21 to 28 days after embryo transfer for the PET Days 21-28 visit. At this visit, the following procedures will occur:

Substance Code Clinical Performance and Safety Investigation of ENDOmetrial Washing
MEdic**al DE**vice Forielle
Protocol Number MS 700623_0009

- Confirm pregnancy via transvaginal ultrasound
- Record the number of gestational sacs present
- Record adverse events, device incidents and concomitant medications
- Schedule the PET Days 70-84/Weeks 10-12 visit

For subjects with no gestational sacs present on transvaginal ultrasound at PET Days 21-28, the investigator will enter a negative result for the PET Days 70-84/Weeks 10-12 obstetric ultrasound (transvaginal or abdominal) and the study exit visit at PET Days 70-84/Weeks 10-12 will be a telephone visit.

7.1.7 Post Embryo Transfer Days 70-84/Weeks 10-12 (Study Exit)

The study exit visit will occur 70 to 84 days (10 to 12 weeks) after embryo transfer. For subjects who are not pregnant at the PET Days 14 or PET Days 21-28 visits, the Days 70-84/Weeks 10-12 visit will be a telephone visit to record adverse events, device incidents, and concomitant medications. The investigator will ensure negative ultrasound results are entered for ultrasounds that were not performed due to the subject not being pregnant.

For subjects with an ongoing pregnancy at the PET Days 21-28 visit, the following assessments will occur at the visit PET Days 70-84/Weeks 10-12 visit:

- Confirm ongoing pregnancy via obstetric ultrasound (transvaginal or abdominal)
- Confirm the number of foetuses, confirm foetal vitality based on the presence of foetal heartbeat(s) and confirm the development of normal pregnancy (assessments to be made for each foetus present on ultrasound)
- Record adverse events, device incidents and concomitant medications

In the event a subject cannot return to the site for the PET Days 70-84 visit, ultrasound report confirming ongoing pregnancy details required (number of foetuses, confirmation of foetal vitality based on the presence of foetal heartbeat and confirmation of the development of normal pregnancy for each foetus present on ultrasound) may be provided to the investigator. In these cases, final study procedures may be performed via telephone and the investigator will enter ultrasound results from the report provided.

7.2 Demographic and Other Baseline Characteristics

At screening, demographics (age, race, ethnicity), BMI, medical history, gynaecological history, infertility history, social history (alcohol, tobacco and illicit drug use), gynaecological exam, and fertility assessment will be performed.

7.3 Clinical Performance Assessments

Clinical Performance of Forielle will be determined by comparing the implantation rate in subjects receiving endometrial washing with Forielle after oocyte retrieval compared to subjects

Substance Code Clinical Performance and Safety Investigation of ENDOmetrial Washing
MEdical DEvice Forielle
Protocol Number MS 700623_0009

who receive no endometrial washing after oocyte retrieval. Clinical performance is defined as behavior of a medical device or response of the subject(s) to that medical device in relation to its intended use, when correctly applied to appropriate subject(s). The primary endpoint of the study is the subject implantation Rate, defined as the number of intrauterine gestational sacs divided by the number of embryos transferred. Additional Forielle clinical performance assessments include the number of pregnancies continuing past the first trimester of pregnancy.

Serum samples will be collected for Estradiol (E₂) and Progesterone (P₄) at the HCG Triggering day to be analysed locally by the centre for the purposes of confirming eligibility criteria (serum P₄ ≤ 1.5 ng/mL and E₂ ≤ 3000 pg/ml). If potential subjects do not meet E₂ and P₄ eligibility criteria, they will be considered screen failures and will not undergo HCG triggering and randomisation within the protocol study conditions. Each site will collect an extra serum sample for P₄ evaluation to be carried out by the central laboratory (PPD [REDACTED]) to validate local laboratory evaluation of P₄ retrospectively to verify subject eligibility and inclusion in planned analyses.

